**Project nº 171-CES/UCP**

**Porto, September 2022**

## Protocol

### Title: O-LIVE: Impact of Portuguese Olive Oil on Biomarkers in Healthy Volunteers

#### Introduction

This research project, approved and funded, is part of a larger project titled "HSoil4Food - Healthy Soil for Food" which encompasses various work packages, one of which is a clinical research project now submitted to this Ethics Committee, titled "O-LIVE: Impact of Portuguese Olive Oil on Biomarkers in Healthy Volunteers".

Olive oil is a millennia-old product that is crucial for social cohesion and local economies in the Mediterranean region, particularly in Portugal [1]. Among the numerous food items, olive oil stands out as one of the most extensively studied in terms of its health benefits and contribution to the prevention of non-communicable chronic diseases [2]. There is ample evidence of the protective effect of olive oil against cardiovascular diseases, diabetes, oncological diseases, and neurological degeneration, the latter being responsible for 8 out of 10 deaths in the Western world [3, 4]. Olive oil has been associated with the reduction of obesity, body weight, body mass index, and waist circumference, which is a reasonable indicator of visceral adiposity [5]. It has also been shown to alter serum lipid profile, decreasing LDL cholesterol and increasing HDL cholesterol [6]. In addition, olive oil has been shown to increase oxidation rate, inhibit lipogenesis, and stimulate lipolysis, as well as affect the expression of receptors involved in weight regulation and fat utilization [7].

The health benefits of olive oil derive from its specific nutritional composition, including monounsaturated fatty acids, polyphenols, and phenolic compounds, which act on metabolism, modulation of inflammatory responses, and gene expression [8]. However, the composition of olive oil can vary considerably depending on the type of olive trees cultivation, soil management practices, as well as extraction and technological processes involved in olive oil production [9]. In the scope of a previous project ("Bio-n2-value - Biological tools to add and defend value in the main agri-food chains", NORTE-01-0145-FEDER-000030), it was demonstrated that similar monovarietal olive oils from different locations in the Trás-os-Montes region revealed different lipid and polyphenolic compositions [10, 11]. These significant differences in olive oil composition may explain the differences found in clinical results.

In this study, we will use an olive oil rich in polyphenols (locally and sustainably produced) and evaluate its effect on various important clinical parameters involved in chronic diseases. We hope that the results of this study will help support the relationship between consumption of olive oil with higher polyphenol content and overall health improvement.

## **Objectives**

The main objective of this study is to evaluate the impact of ingestion of polyphenol-rich olive oil on important clinical parameters, such as anthropometric measurements, blood and urinary biomarkers, gene expression, and gut microbiota composition. To achieve this objective, a quasi-experimental clinical study will be conducted with the following tasks:

- 1) Recruitment of participants;
- 2) Intervention;
- 3) Periodic evaluation of the impact of olive oil ingestion on clinical parameters of participants, through:
  - 3.1) Administration of questionnaires;
  - 3.2) Anthropometric measurements;
  - 3.3) Analysis of blood biomarkers;
  - 3.4) Analysis of urinary biomarkers;
  - 3.5) Analysis of gene expression;
  - 3.6) Analysis of gut microbiota.

## **Methodology**

This project will be carried out at the Center for Biotechnology and Fine Chemistry (CBQF) and at the School of Biotechnology of the Catholic University of Portugal, Porto campus.

### Task 1 - Recruitment of Participants

This project consists of a quasi-experimental clinical study, whose target population is healthy adult volunteers. Participants will be recruited among men and women, aged 18 years or older, who are healthy and belong to the community of the Catholic University

of Portugal (Porto) and do not meet any of the exclusion criteria (described in the questionnaire). Individuals will be invited to participate voluntarily in this study, receiving detailed information about the research to allow for an informed and free decision. Individuals who agree to participate will sign an informed consent.

### Task 2 - Intervention

Participants will include in their usual diet the daily intake of 30 mL of polyphenol-rich olive oil (intervention group) for 3 months. At the beginning (day 1), midpoint (between days 40 and 50), and end of the intervention period (day 90), participants will be assessed. The olive oil will be placed in dark-colored containers to minimize loss of phenolic content due to sunlight. The containers with the olive oil will be provided free of charge to participants at the beginning of each intervention period. Participants' adherence to olive oil intake will be verified through two processes: 1) by returning the containers at the end of each intervention period for the measurement and recording of the daily amount of unconsumed olive oil; 2) by quantifying hydroxytyrosol by GC-MS or LC-MS in 24-hour urine samples collected from participants who agree to this urine collection.

### Task 3 - Periodic evaluation of the impact of olive oil intake

To investigate the impact of olive oil intake, participants will be evaluated at three established time points: at the beginning (day 1), midpoint (between days 40 and 50), and end of the intervention period (day 90). This evaluation will be performed by healthcare professionals and will consist of administering a standardized and validated questionnaire in person to obtain information on olive oil intake, dietary habits, and physical activity level.

#### Task 3.1 - Administration of Questionnaires

A standardized and validated questionnaire will be administered in person to participants to obtain information on olive oil intake, dietary habits, and physical activity level.

#### Task 3.2 - Anthropometric Measurements

Anthropometric measurements, obtained according to standardized protocols, include the measurement of height, body weight, waist circumference (WC), and collection of body composition data. Height and weight will be measured with a stadiometer and a scale, respectively, with participants barefoot. Waist circumference will be measured at the midpoint between the last rib and the iliac crest using a flexible measuring tape. Body composition data, including fat mass and lean body mass, will be collected through

bioelectrical impedance analysis (BIA). Body mass index (BMI) will also be calculated by dividing weight by height squared. In addition to anthropometric measurements systolic and diastolic blood pressure will be measured using a sphygmomanometer after the participant has rested for 5 minutes.

### Task 3.3 - Analysis of Blood Biomarkers

This task aims to assess the impact of olive oil consumption on various blood biomarkers through the analysis of capillary blood samples. Capillary blood will be collected from a finger of the hand using a single-use lancet at three timepoints during the intervention study. The capillary blood samples (volume in  $\mu\text{L}$ ) will be analyzed using the cobas® b101 device (Roche), a Point of Care equipment that allows for rapid quantitative measurement of glycated hemoglobin (HbA1c), estimated average glucose (eAG), triglycerides (TG), total cholesterol (CHOL), high-density lipoprotein cholesterol (HDL), low-density lipoprotein cholesterol (LDL), atherogenic index (CHOL/HDL), and C-reactive protein. These data will be used to calculate the visceral adiposity index (VAI) using the formulas described below:

- Male VAI : 
$$\left[ \frac{WC \text{ (cm)}}{\left\{ 39.68 + (1.88 \times BMI \left( \frac{\text{kg}}{\text{m}^2} \right)) \right\}} \right] \times \left[ \frac{TG(\text{mmol/l})}{1.03} \right] \times \left[ \frac{1.31}{HDL(\text{mmol/l})} \right]$$
- Female VAI : 
$$\left[ \frac{WC \text{ (cm)}}{\left\{ 36.58 + (1.89 \times BMI \left( \frac{\text{kg}}{\text{m}^2} \right)) \right\}} \right] \times \left[ \frac{TG(\text{mmol/l})}{0.81} \right] \times \left[ \frac{1.52}{HDL(\text{mmol/l})} \right]$$

VAI: Visceral Adipose Index, WC: Waist Circumference, BMI: Body Mass Index, TG: Triglyceride, HDL: High Density Lipoprotein

### Task 3.4 - Analysis of Urinary Biomarkers

This task aims to assess the impact of olive oil consumption on the urinary concentration of 8-hydroxy-2'-deoxyguanosine (8OHdG), a biomarker of oxidative DNA damage. Urine will be collected in a 100 mL container, and the concentration of 8OHdG will be quantified using an enzyme-linked immunosorbent assay (ELISA) method with commercially available kits. In addition, the concentration of creatinine in the corresponding urine samples will be determined using a colorimetric kit to normalize the urinary concentration of 8OHdG.

### Task 3.5 - Analysis of Gene Expression

A buccal smear sample will be collected for subsequent DNA extraction and real-time quantitative PCR (Polymerase Chain Reaction) to determine the expression of selected genes, such as SOD1, CCL2, and NFkB, involved in inflammation and oxidative stress.

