#### **Task 3.6 - Analysis of Intestinal Microbiota**

This task aims to evaluate the impact of olive oil intake on the composition of the intestinal microbiota through the analysis of fecal samples. Bacterial populations in fecal cultures will be analyzed by extracting microbial DNA and applying real-time quantitative PCR using specific primers based on 16S rRNA gene sequences. The impact on the metabolic activity of the intestinal microbiota will be evaluated in fecal supernatants in terms of: a) quantification of short-chain fatty acids and lactic acid by HPLC-UV, according to Gullon et al. [13]; b) quantitative analysis of the disappearance of important bioactive compounds previously identified in olive oil and the corresponding formation of metabolites using GC-MS/GC-FID.

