#### **Future Perspectives**

With this project, we expect to identify whether olive oil with this lipid profile, phenolic content, and antioxidant properties modifies and impacts important serum biomarkers, including lipid and anti-inflammatory profiles, blood pressure, as well as anthropometric variables and intestinal microbiota composition. These results will help clarify the nature of the relationship between polyphenol-rich olive oil and health indicators. The definition of an effective dose of olive oil for shaping certain biomarkers and health indicators based on its polyphenol composition may be of great importance in nutritional therapy and may constitute an alternative approach for prevention and management of different chronic diseases. The results will be disseminated to various audiences, ranging from the academic community (scientific journal manuscripts), healthcare professionals (nutritional counseling), to the general public (mainstream media).

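### Task 3.5 sets out to measure gene expression by quantitative PCR on extracted DNA, with no RNA extraction or reverse transcription, so the outcome cannot be obtained as written

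*Combined protocol and SAP*

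**What the plan says.** The assay is described in one place only, the single sentence of Task 3.5. A "buccal smear sample will be collected for subsequent DNA extraction and real-time quantitative PCR", and the aim is "to determine the expression of selected genes, such as SOD1, CCL2, and NFkB, involved in inflammation and oxidative stress".

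The outcome is not incidental to the protocol. The main objective covers "anthropometric measurements, blood and urinary biomarkers, gene expression, and gut microbiota composition", and the list of periodic evaluations that follows contains "3.5) Analysis of gene expression" as a task of its own. The Introduction gives a biological reason for it, describing components of olive oil "which act on metabolism, modulation of inflammatory responses, and gene expression".

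The next task, on gut microbiota, also pairs DNA with PCR. It proceeds by "extracting microbial DNA and applying real-time quantitative PCR using specific primers based on 16S rRNA gene sequences".

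The SAP names no analysis for gene expression and no normalisation for it. The Future Perspectives section expects to learn whether the oil "modifies and impacts important serum biomarkers, including lipid and anti-inflammatory profiles, blood pressure, as well as anthropometric variables and intestinal microbiota composition", a list in which gene expression does not appear.

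**The concern.** The analyte named in Task 3.5 does not match the outcome named in the same sentence. Expression of a gene is the quantity of its transcript. PCR amplifies DNA, so to measure transcripts the laboratory must extract RNA and convert it to complementary DNA by reverse transcription. Without that conversion, the signal from extracted DNA reflects how many copies of the gene are in the tube. A participant's copy number for genes such as SOD1 or CCL2 is not expected to respond to three months of olive oil. Differences between visits would mostly reflect how much material the smear yielded, plus assay noise.

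At stake is one named component of the main objective. With data of this kind, neither an effect of the oil on these genes nor the absence of one could be concluded. There is also a timing risk. Task 3 sets evaluations at day 1, between days 40 and 50, and at day 90. If the buccal smear follows that schedule (Task 3.5 does not say), a day 1 sample handled only for DNA cannot be replaced once intake has begun.

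**Working it through.** There is no figure to reproduce: the documents attach no sample size, effect size or power to this outcome. The check is a comparison of the text with what the assay can deliver.

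**Step 1. What is to be measured.** Task 3.5, by its heading and its stated purpose, and the Objectives, in the main objective and in item 3.5, all say expression. The target is therefore transcript abundance in the participant's own cells.

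**Step 2. What the written steps produce.** Task 3.5 gives three steps: buccal smear, DNA extraction, real-time quantitative PCR. Their product is a gene-copy measurement. Dividing by a reference gene measured in the same DNA would correct for the amount of material, but the result would still be a ratio of gene copies.

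**Step 3. Whether another section supplies the missing step.** A case-sensitive count over the protocol and SAP text gives:

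| Term | Occurrences | Where |
|---|---|---|
| RNA | 1 | Task 3.6, within 16S rRNA |
| mRNA | 0 | – |
| cDNA | 0 | – |
| reverse transcription | 0 | – |
| RT-qPCR | 0 | – |

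The one hit names a bacterial gene used as a primer target on DNA from fecal samples. It has nothing to do with host transcripts in a buccal smear.

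**Step 4. The two PCR tasks side by side.**

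| | Task 3.5 | Task 3.6 |
|---|---|---|
| Sample | buccal smear | fecal sample |
| Nucleic acid extracted | DNA | microbial DNA |
| Quantity sought | expression of host genes | bacterial populations |
| Does DNA-based PCR give it? | no | yes |

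The method in the two columns is essentially the same. It suits Task 3.6, where counting copies of a bacterial gene is the point. It does not suit Task 3.5.

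**Step 5. Whether the gap comes from extraction or redaction.** The sentence in Task 3.5 is complete and names the nucleic acid explicitly. Nothing in it is blacked out or broken.

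**Result.** The outcome named in Task 3.5 does not follow from the steps in Task 3.5, and no other section closes the gap.

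**The case against.** The strongest reply is that this is a slip of wording. The heading, the purpose and the objective all say expression; only one word conflicts. The next task correctly pairs DNA extraction with PCR, so the wording may have carried over. Portuguese remnants in the reference list also make a translation error plausible. Moreover, the protocol is a short text for an ethics committee and its other assays are described just as briefly: Task 3.4 refers only to commercial kits, and Task 2 leaves the mass spectrometry method open. At that level of detail, silence on reverse transcription proves little.

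Much of this stands. The documents cannot distinguish a slip from a real plan, and silence alone would be weak evidence. But Task 3.5 is not merely silent. It names an analyte, that analyte is the wrong one for the stated outcome, and the choice of extraction kit and sample preservation depends on it. A slip at this point still needs correcting.

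A second reply is that correcting the assay would not by itself allow a conclusion about the oil, because the protocol describes only an intervention group and the SAP names no analysis for gene expression. That is fair, and it limits how much this one correction can achieve. It does not make DNA-based PCR capable of measuring expression.

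A third reply is that the weight is low. No primary outcome is designated, and the other evaluation tasks do not depend on this step. That also stands, and it keeps the point from being rated more severely. Against it, the outcome is part of the main objective.

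**Conclusion.** The concern holds as stated. Task 3.5 as written measures gene copies and cannot yield the expression outcome that it and the Objectives name.

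The size is one evaluation task of six (3.1 to 3.6) and the three genes given as examples. No numerical bias is claimed. The other outcomes do not rest on this step and were not assessed for this point. It should be fixed, but it does not threaten the rest of the study.

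Confidence is high for the text and does not extend to laboratory practice. The conclusion rests on reading the protocol literally: if the laboratory already extracts RNA and reverse-transcribes it, the data are sound in this respect and only the document is wrong.

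**What to change.** In Task 3.5, replace the DNA extraction and PCR step with RNA extraction, reverse transcription and real-time quantitative PCR, normalised to a reference gene. State that the buccal sample is collected and stored so that RNA is preserved. The minimum needed to remove the contradiction is to state which nucleic acid is extracted and that reverse transcription is done; the reference gene and preservation wording go further, but are needed for the result to be interpretable.

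If only DNA is or was collected, or if RNA from a buccal smear proves unusable, remove or rename the gene-expression outcome in both the Objectives and Task 3.5.

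If the wording is a slip, or the outcome is removed or renamed, the cost is a text change. If the laboratory did plan to work from DNA, the cost is different kits and sample handling, and possibly some samples from which usable RNA cannot be obtained. That last item is an assumption, since the documents give no yield data. The laboratory's actual procedure should be confirmed before any sample is taken or, if sampling has begun, before any result is reported as expression.

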#### **Task 3.6 - Analysis of Intestinal Microbiota**

This task aims to evaluate the impact of olive oil intake on the composition of the intestinal microbiota through the analysis of fecal samples. Bacterial populations in fecal cultures will be analyzed by extracting microbial DNA and applying real-time quantitative PCR using specific primers based on 16S rRNA gene sequences. The impact on the metabolic activity of the intestinal microbiota will be evaluated in fecal supernatants in terms of: a) quantification of short-chain fatty acids and lactic acid by HPLC-UV, according to Gullon et al. [13]; b) quantitative analysis of the disappearance of important bioactive compounds previously identified in olive oil and the corresponding formation of metabolites using GC-MS/GC-FID.

#### **Future Perspectives**

With this project, we expect to identify whether olive oil with this lipid profile, phenolic content, and antioxidant properties modifies and impacts important serum biomarkers, including lipid and anti-inflammatory profiles, blood pressure, as well as anthropometric variables and intestinal microbiota composition. These results will help clarify the nature of the relationship between polyphenol-rich olive oil and health indicators. The definition of an effective dose of olive oil for shaping certain biomarkers and health indicators based on its polyphenol composition may be of great importance in nutritional therapy and may constitute an alternative approach for prevention and management of different chronic diseases. The results will be disseminated to various audiences, ranging from the academic community (scientific journal manuscripts), healthcare professionals (nutritional counseling), to the general public (mainstream media).

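### The SAP names no analysis of within-person change, and a one-group, one-oil, one-amount design cannot by itself attribute such change to the oil, its polyphenols or a dose

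*Combined protocol and SAP*

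**What the plan says.** **Design.** Task 1 states: "This project consists of a quasi-experimental clinical study, whose target population is healthy adult volunteers". Task 2 gives every participant the same polyphenol-rich oil, 30 mL daily for 3 months, added to the usual diet. Tasks 2 and 3 set three assessments: day 1, days 40–50 and day 90. No control oil, untreated group, crossover or run-in is described. Task 2 does label the participants an *intervention group* and twice refers to *each* intervention period, although it describes only one group and one period.

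**Aim.** The Objectives section says: "The main objective of this study is to evaluate the impact of ingestion of polyphenol-rich olive oil on important clinical parameters". The Introduction says "we will use an olive oil rich in polyphenols (locally and sustainably produced) and evaluate its effect on various important clinical parameters" and hopes that the results will "help support the relationship between consumption of olive oil with higher polyphenol content and overall health improvement". Future Perspectives says "we expect to identify whether olive oil with this lipid profile, phenolic content, and antioxidant properties modifies and impacts important serum biomarkers". It also raises a dose prospect, in a sentence that begins "The definition of an effective dose of olive oil for shaping certain biomarkers and health indicators based on its polyphenol composition may be of" and continues that this may be of great importance in nutritional therapy. Results are meant for academics, healthcare professionals and the public.

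**Analysis.** The SAP names a baseline comparison by Mediterranean-diet adherence, a general comparison by 95% confidence intervals, correlations between parameters, optional linear regression between parameters, logistic regression relating clinical to anthropometric parameters, and a 0.05 significance threshold.

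**The concern.** The objective is about what happens to participants while they take the oil. With three visits per person and no comparator, the design can estimate within-person change from day 1. The SAP does not name that analysis. The analyses it does name describe how participants differ at baseline or how parameters relate to one another. The contrast that would carry the main result, including its visit, model and outcome, is therefore open to choice after the data are seen.

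The second issue is interpretation. In a single group, any average shift over 90 days that has nothing to do with the oil is part of the before-after difference. Asking whether oil of this composition modifies biomarkers is a causal question, and this design cannot settle it. The documents do not say so, although the findings are intended to reach nutritional counselling and mainstream media.

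**Working it through.** The documents give no sample size, SD, effect size or power, so there is no stated figure to reproduce. The check is mainly a comparison of texts.

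**1. Assigned contrasts (Tasks 1–3).** Groups: 1. Oils: 1. Amounts: 1. Assigned contrasts on oil versus no oil: 0; on polyphenol content: 0; on amount: 0. Actual intake may vary and is measured through returned containers and, in those who agree, urinary hydroxytyrosol. That variation is chosen by participants, not assigned, and the SAP names no intake-response analysis.

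**2. The SAP, sentence by sentence.**

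| Sentence | What it names | Change from day 1? |
|---|---|---|
| 1–2 | Baseline characteristics by diet adherence; one-way ANOVA, chi-squared | No |
| 3 | All data compared by 95% CI; no visit, pairing or contrast given | Not stated |
| 4–5 | Pearson or Spearman correlations between parameters | No |
| 6 | Linear regression, optional, between parameters; no time term or person effect | Not stated |
| 7 | Logistic regression, clinical with anthropometric parameters | No |
| 8 | Significance threshold of 0.05 | No |

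Sentences naming a change, a follow-up visit, pairing or repeated measures: 0 of 8. Planned visits: 3.

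**3. Why pairing needs stating.** With equal variances and within-person correlation ρ, the variance of a mean change is 2σ²(1 − ρ)/n. Treating the visits as independent gives 2σ²/n. The ratio of standard errors is 1/√(1 − ρ). The value of ρ is assumed: at 0.5 the ratio is 1/√0.5 = 1.41, and at 0.8 it is 1/√0.2 = 2.24. Whether *compared using 95% CI* means paired or unpaired intervals could therefore alter interval width by about that factor.

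**4. Why a significant change is not attribution (illustration only).** Suppose the oil has no effect, but values drift by d standard deviations for other reasons. A two-sided paired t-test at 0.05 then has noncentrality √n × d/√(2(1 − ρ)). For example, with n = 60, ρ = 0.5 and d = 0.2, it is √60 × 0.2/√1 = 1.55, and the rejection probability is 0.332. All of n, d and ρ are assumptions. Across d = 0.1 to 0.3 and ρ = 0.5 to 0.8:

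| n | Probability of a significant change |
|---|---|
| 30 | 0.083 to 0.709 |
| 60 | 0.119 to 0.951 |
| 100 | 0.168 to 0.997 |

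With d = 0 it is 0.05. The test is valid for change. It says nothing about the cause, and a larger n makes an unrelated drift easier to detect.

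**The case against.** **The documents do not assert a causal conclusion.** This stands. A reader might infer that the protocol has already committed to reporting the before-after difference as the oil's effect. It has not: Objectives states an aim, Future Perspectives asks an open *whether* question, and it then speaks only of clarifying a relationship. The point is that the question is causal and the limit on answering it is unstated.

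**The dose sentence is only a prospect.** This also stands. It sits under Future Perspectives, is hedged, and is not an objective. A reader might take it as a planned dose finding; the text does not support that.

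**The design is disclosed as quasi-experimental.** True, and a single-group study is legitimate. But the label conveys non-randomisation. It neither supplies a comparator nor tells readers what cannot be concluded.

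**A comparator may exist.** The Task 2 wording could point to an undescribed group or period, or *each* period could mean the intervals between visits. The text does not say, so neither a hidden arm nor its absence should be presumed in the remedy.

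**The SAP could accommodate a change analysis.** The confidence-interval sentence and the optional regression do not rule one out, but neither names one.

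**Diet and activity are recorded.** Measured changes could be partly adjusted for. Common time trends and unmeasured changes could not.

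**Conclusion.** The concern holds in two parts. The stronger is the SAP gap: 0 of 8 sentences specify the within-person change that three visits are scheduled to measure, and the analyses that are specified would not estimate it. The second is that attribution to the oil, its polyphenols or a dose cannot be settled without a comparator, and the protocol does not state this limit. This rests on reading Task 2 as describing one group and one period, which is all that the text describes. If a second group or period was intended, the attribution part changes, but the SAP would still need to name the contrast. No claim is made about how large any non-oil change would be. The drift figures rest wholly on assumed inputs. The matter should be corrected before analysis; it is not a reason to redesign the study.

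**What to change.** 1. **Task 2, first.** Clarify whether the *intervention group* label and *each* intervention period refer to a group or period not described. If so, describe it and analyse that contrast.

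2. **SAP.** Add:

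> For each outcome measured at day 1 and later, within-person change from day 1 to day 90 (main contrast) and from day 1 to days 40–50 will be estimated with a repeated-measures model (visit as a factor, participant as a random effect) and reported with a 95% CI. A secondary estimate will adjust for recorded physical activity and diet other than olive oil intake.

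Name one primary outcome in advance and label the rest exploratory; otherwise selection across outcomes stays open. Olive oil intake must be left out of the adjustment because the same questionnaire records it, and adjusting for it could remove the exposure itself.

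3. **Objectives and Future Perspectives, if there is only one group.** Add to each:

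> This single-group study estimates change during daily intake of this olive oil; without a comparator, change cannot be firmly attributed to the oil rather than to time or unmeasured factors, to its polyphenols rather than the rest of the oil, or to a dose.

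Rewording the title and task headings is optional.

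**Cost.** If there is one group, this is text only: no new arm, visit, sample or participant. The stated claim becomes weaker and the SAP slightly longer. Diet after day 1 may itself respond to the oil, so the adjusted estimate is secondary and does not remove the attribution limit.
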